#### **4.6. Follow-Up Phase**

##### **4.6.1. Safety Follow-Up Visit**

The mandatory Safety Follow-Up Visit should be conducted approximately 30 days after the last dose of study treatment or before the initiation of a new anti-cancer treatment, whichever comes first. All AEs that occur prior to the Safety Follow-Up Visit should be recorded. Subjects with an AE of Grade > 1 will be followed until the resolution of the AE to Grade 0-1 or until the beginning of a new anti-neoplastic therapy, whichever occurs first. SAEs that occur within 30 days of the final dose on the study or before initiation of a new anti-cancer treatment should also be followed and recorded. Subjects who are eligible for retreatment with pembrolizumab (as described in Section 4.8) may have up to two safety follow-up visits, one after the Treatment Period and one after the Second Course Phase.

##### **4.6.2. Follow-Up Period**

Subjects who discontinue study treatment for a reason other than disease progression will move into the Follow-Up Phase and should be assessed every 9 weeks ( $\pm$  7 days) by radiologic

imaging to monitor disease status. Every effort should be made to collect information regarding disease status until the start of new anti-neoplastic therapy, disease progression, death, end of the study or if the subject begins retreatment with pembrolizumab as detailed in Section 4.8, Second Course Phase. Information regarding post-study anti-neoplastic treatment will be collected if new treatment is initiated.

Subjects who are eligible to receive retreatment with pembrolizumab according to the criteria in Section 4.8, Second Course Phase (Retreatment Period), will move from the Follow-up Phase to the Second Course Phase when they experience disease progression.

#### 4.6.3. **Survival Follow-Up**

Once a subject experiences confirmed disease progression or starts a new anti-cancer therapy, the subject moves into the survival follow-up phase and should be contacted by telephone every 12 weeks (~ 3 months) to assess for survival status until death, withdrawal of consent, or the end of the study, whichever occurs first.

#### 4.7. **Unscheduled Visits**

Unscheduled study visits with the study team may occur at any time if medically warranted. Any assessments performed at those visits should be recorded in the eCRF.

#### 4.8. **Second Course Phase**

Subjects who stop pembrolizumab and epacadostat with SD or better may be eligible for up to one year of additional pembrolizumab and epacadostat therapy if they progress after stopping study treatment. This retreatment is termed the Second Course Phase of this study and is only available if the study remains open and the subject meets the following conditions:

- **Either**
  - Stopped initial treatment with pembrolizumab and epacadostat after attaining an investigator-determined confirmed CR according to RECIST 1.1, and
    - Was treated for at least 24 weeks with pembrolizumab before discontinuing therapy.
    - Received at least two cycles of treatment with pembrolizumab and epacadostat beyond the date when the initial CR was declared.

**OR**

- Had SD, PR or CR and stopped pembrolizumab and epacadostat treatment after 24 months of study therapy for reasons other than disease progression or intolerability.

**AND**

- Experienced an investigator-determined confirmed radiographic disease progression after stopping their initial treatment with pembrolizumab
- Did not receive any anti-cancer treatment since the last dose of pembrolizumab
- Has an ECOG performance status of 0 or 1
- Demonstrates adequate organ function as defined by the eligibility criteria Section 3.3.
- Female subject of childbearing potential should have a negative serum or urine pregnancy test within 3 days prior to receiving retreatment with study medication.
- Female subject of childbearing potential should be willing to use 2 methods of birth control or be surgically sterile, or abstain from heterosexual activity for the course of the study through 120 days after the last dose of study medication. Subjects of child bearing potential are those who have not been surgically sterilized or have been free from menses for > 1 year.
- Male subject should agree to use an adequate method of contraception starting with the first dose of study therapy through 120 days after the last dose of study therapy.
- Does not have a history or current evidence of any condition, therapy, or laboratory abnormality that might interfere with the subject's participation for the full duration of the study or is not in the best interest of the subject to participate, in the opinion of the treating investigator.

Subjects who restart treatment will be retreated at the same dose and dose interval as when they last received pembrolizumab and epacadostat. Treatment will be administered for up to one additional year. Visit requirements are outlined in Section 9, schedule of events calendar.

## **4.9. Study Assessments and Procedures**

### **4.9.1. Safety Assessments**

#### **4.9.1.1. Adverse Events**

The investigator or qualified designee will assess each subject to evaluate for potential new or worsening AEs as specified in the schedule of events calendar and more frequently if clinically indicated. Adverse experiences will be graded and recorded throughout the study and during the follow-up period according to NCI CTCAE Version 5. Toxicities will be characterized in terms regarding seriousness, causality, toxicity grading, and action taken with regard to study treatment.

Please refer to Section 7 for detailed information regarding the assessment and recording of AEs.

Adverse events will be monitored from the time the subject begins treatment. Subjects will be instructed to report all AEs during the study and will be assessed for the occurrence of AEs throughout the study. In order to avoid bias in eliciting AEs, subjects will be asked general, non-leading questions such as "How are you feeling?" All AEs (serious and nonserious) must be recorded on the source documents and eCRFs regardless of the assumption of a causal relationship with the study drug. The definition, reporting, and recording requirements for AEs are described in Section 7.

All AEs of unknown etiology associated with epacadostat and pembrolizumab exposure should be evaluated to determine if it is possibly an AE of a potentially immunologic etiology. See Section 7 regarding the identification, evaluation, and management of AEs of potential immunological etiology.

Events of clinical interest (ECI) identified after signing consent through 100 days following cessation of treatment, regardless of initiation of new anticancer therapy, must be reported to Merck and Incyte within 10 days of the event.

Subjects should be assessed for possible ECIs prior to each dose. Laboratory results should be evaluated and subjects should be asked for signs and symptoms suggestive of an irAE. Subjects who develop an ECI thought to be immune-related should have additional testing to rule out other etiologic causes. If laboratory results or symptoms indicate a possible immune-related

ECI, then additional testing should be performed to rule out other etiologic causes. If no other cause is found, then it is assumed to be immune-related.

#### 4.9.1.2. **Comprehensive Physical Examination**

The investigator or qualified designee will perform a complete physical exam during the screening period. Clinically significant abnormal findings should be recorded as medical history. A full physical exam should be performed during screening,

The comprehensive physical examination will include the following organ or body system assessments: skin, head, eyes, ears, nose, and throat, thyroid, lungs, cardiovascular system, abdomen (liver, spleen), extremities, lymph nodes, and a brief neurological examination. Before the first dose of study treatment, clinically significant abnormal findings should be recorded as medical history. After the first dose of study treatment, new clinically significant abnormal findings should be recorded as AEs.

#### 4.9.1.3. **Targeted Physical Examination**

For cycles that do not require a full physical examination per the schedules of assessments, the investigator or qualified designee will perform a directed physical examination as clinically indicated before study treatment administration. A targeted physical examination will be a symptom-directed evaluation conducted by the investigator or designee. The targeted physical examination will include assessment(s) of the body systems or organs, as indicated by subject symptoms, AEs, or other findings. New clinically significant abnormal findings should be recorded as AEs.

#### 4.9.1.4. **Vital Signs**

The investigator or qualified designee will take vital signs at screening, prior to the administration of each dose of pembrolizumab treatment, and at treatment discontinuation as specified in the schedule of events calendar (Section 9). Vital signs should include temperature, pulse, respiratory rate, weight and blood pressure. Height will be collected at Cycle 1 Day 1 only.

#### 4.9.1.5. **Twelve-Lead Electrocardiograms (ECGs)**

Baseline ECG will be obtained during screening period prior to the first dose of epacadostat. Subsequent ECGs will be obtained as clinically indicated and at EOT. Clinically significant

abnormal findings prior to beginning therapy should be recorded as medical history. Clinically significant abnormal findings after beginning therapy or changes from baseline should be recorded as AEs.

The 12-lead ECG will be interpreted by the investigator at the site and will be used for immediate subject management. The decision to include or exclude a subject or withdraw a subject from the study based on an ECG flagged as "Abnormal, Clinically Significant" is the responsibility of the investigator, as appropriate. The correction method (Fredericia or Bazett) used for calculating QTc will need to be provided in the eCRF.

#### 4.9.1.6. **Laboratory Assessments**

Details regarding specific laboratory procedures/assessments to be performed in this study are provided below (hematology, chemistry and urinalysis). Laboratory tests should be conducted up to 2 days prior to dosing. If laboratory tests at screening are done within 7 days of Cycle 1 Day 1 they do not need to be repeated at that visit. Results must be reviewed by the investigator or qualified designee and found to be acceptable prior to each dose of study treatment.

##### Hematology, Lipid Panel, Coagulation Panel, Serology, and Endocrine Function Testing

Hematology, lipid panel, coagulation panel, and endocrine function will all be analyzed by the site laboratory prior to beginning treatment. Any subjects on coumadin-based anticoagulants that need weekly INR monitoring for the first 4 weeks with initiation of treatment will perform the INR testing locally. These labs should be drawn as 12 hour fasting. See Table 2 for more details about specific tests that need to be collected.

##### Tumor tissue sample molecular testing

Tumor molecular profiling will be performed on archival or newly obtained tumor tissue. These tests can be historical or obtained during the course of the study.

##### Urinalysis

Urinalysis will be analyzed by the site laboratory.

### Serum Chemistry and Liver Function Tests

All serum chemistry testing (screening, Cycle 1 Day 1, and Day 1 of each cycle) will be performed fasting by the site's laboratory, as well as any additional LFT monitoring if it is required. Liver function test monitoring for persistent low-grade abnormalities does not need to be monitored twice a week indefinitely. Appropriate LFT monitoring intervals should be discussed with Merck and Incyte for these circumstances.

### Pregnancy Testing

Serum or urine pregnancy tests will be analyzed by the site laboratory during screening and must be within 3 days before first dose of study treatment. Subsequently, pregnancy tests will be conducted only as medically indicated.

If a subject inadvertently becomes pregnant while on treatment with epacadostat and pembrolizumab, the subject will immediately be withdrawn from the study. The site will contact the subject at least monthly and document the subject's status until the first well-baby visit to determine outcome, including spontaneous or voluntary termination, details of the birth, and the presence or absence of any birth defects, congenital abnormalities, or maternal and/or newborn complications. The outcome of the pregnancy will be reported without delay and within 24 hours if the outcome is an SAE (e.g., death, abortion, congenital anomaly, or other disabling or life-threatening complication to the mother or newborn). The study investigator will make every effort to obtain permission to follow the outcome of the pregnancy and report the condition of the fetus or newborn. If a male subject impregnates his female partner, the study personnel at the site must be informed immediately and the pregnancy reported and followed as described above and in Section 7.

**Table 2: Required Laboratory Tests**

Hematology	Chemistry	Urinalysis	Other
Hematocrit	Albumin	Blood	Serum $\beta$ -human chorionic gonadotropin†
Hemoglobin	Alkaline phosphatase	Glucose	PT/INR
Platelet count	Alanine aminotransferase (ALT)	Protein	aPTT
White Blood Cell Count (total and differential)	Aspartate aminotransferase (AST)	Specific gravity	Total triiodothyronine (T3) (if applicable)
Red Blood Cell Count	Lactate dehydrogenase	Urine pregnancy test †	Free thyroxine (T4) (if

Hematology	Chemistry	Urinalysis	Other
	(LDH)		applicable)
Absolute Neutrophil Count	Carbon Dioxide (CO 2 or bicarbonate)		Thyroid stimulating hormone (TSH)
Absolute Lymphocyte Count			Blood for correlative studies and future research
	Uric Acid		
	Calcium		
	Chloride		
	Glucose		
	Phosphorus		
	Potassium		
	Sodium		
	Magnesium		
	Total Bilirubin		
	Direct Bilirubin ( If total bilirubin is elevated above the upper limit of normal )		
	Total protein		
	Blood Urea Nitrogen		
† Perform on women of childbearing potential only. If urine pregnancy results cannot be confirmed as negative, a serum pregnancy test will be required.			

#### 4.9.2. Efficacy Assessments – Tumor Imaging During the Study

Initial tumor imaging must be performed within 28 days before the first planned dose of study treatment. The site study team must review pre-study images to confirm the subject has measurable disease per RECIST v1.1 for solid tumors and irRC. A standard, full assessment for lesions should be conducted at baseline, including CT or MRI scans of chest, abdomen, and pelvis for solid tumors. The same modality (CT and/or MRI) should be used for follow-up assessments every 9 weeks, including radiological assessments of all sites of disease present at baseline unless otherwise medically indicated. In addition to radiological monitoring, all other lesions observed at the screening visit should be followed. Baseline scan must be a contrast computed tomography (CT) with contrast of the chest/abdomen/pelvis, except in circumstances where there is a contrast allergy.

Tumor imaging may be performed by CT and/or MRI, but investigator should do their best, as medically appropriate, to keep with the same imaging technique per subject throughout the

study. Scans must be a contrast CT and/or MRI, except in circumstances where there is a contrast allergy. Imaging should be performed every 9 weeks ( $\pm$  7 days) or more frequently if clinically indicated. Imaging should not be delayed for delays in cycle starts or extension of combination treatment cycle intervals.

Per irRC, response should be confirmed by a repeat radiographic assessment not less than 4 weeks from the date the response was first documented. The scan for confirmation of response may be performed at the earliest 4 weeks after the first indication of response, or at the next scheduled scan (9 weeks later), whichever is clinically indicated.

Imaging should continue to be performed until documented disease progression, the start of new anticancer treatment, withdrawal of consent, death, or the end of the study, whichever occurs first. Disease progression should be confirmed at least 4 weeks after the first scan indicating progressive disease in clinically stable subjects. Subjects who have unconfirmed disease progression may continue on treatment until progression is confirmed provided they have met the conditions detailed in Section 10.

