##### 4.3.7.3. **Subsequent Anti-Cancer Therapy Status**

The investigator or qualified designee will review all new anti-neoplastic therapy initiated after the last dose of study treatment. If a subject initiates a new anti-cancer therapy within 30 days after the last dose of study treatment, the 30-day Safety Follow-up visit must occur before the first dose of the new therapy. Once new anti-cancer therapy has been initiated, the subject will move into survival follow-up.

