## 12. STATISTICS CONSIDERATIONS

### 12.1. Statistical Design

This is a single-stage study for the doublet epacadostat and pembrolizumab. A 6-month PFS of 20% was observed using single agent pembrolizumab and is the basis for the null hypothesis of the present study (Bang, abstract 4001, GI ASCO 2015). We will enroll 30 patients over 18 months and follow patients for at least 6 months. This design has 80% power to reject a 20% PFS rate, if the true PFS is 39%. Calculation based on binomial probabilities with a one-sided significance of 10%. The level of significance for the primary endpoint in Phase 2 is one-sided 10%, which is deemed acceptable for a proof-of-concept study.

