## 12.2. Safety Analyses

### 12.2.1. Analysis Plan

The analysis will be done on the intent to treat population and patients who drop out will be censored at the point of last follow up.

The primary endpoint of the study is 6-month Progression-free survival (PFS), which is defined as number of days from the first day of taking study dose to the earlier of death or disease progression by RECIST v1.1 for solid tumors. Median PFS will be estimated using the Kaplan-Meier method.

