### 12.3. Secondary Analyses

Secondary efficacy analysis will be conducted for the efficacy evaluable population. Secondary endpoints and analyses are as follows:

To evaluate response rate (RR). Response will be determined by RECIST v1.1 for solid tumors. The 95% exact CI for the RR will be estimated using the Clopper-Pearson method. For objective responders, the duration of response is the time from the first objective response contributing to an objective response, to the first objective response of PD (by RECIST v1.1) occurring after the first objective response contributing to the objective response.

To evaluate overall survival (OS). Time-to-event data will be analyzed by the Kaplan-Meier method, treating subjects with no observed death or progression as censored at their last date known to be alive. For the OS analysis, the nonparametric Kaplan-Meier method will be used to estimate the survival time distribution and the median survival.

To assess the safety and tolerability of epacadostat in combination with pembrolizumab. AEs will be coded by the MedDRA, and incidences will be tabulated by preferred term and system organ class for all events, related events, and events  $\geq$  Grade 3. Severity of AEs will be based on the CTCAE v5 scale as indicated. Quantitative safety variables and their changes from baseline (laboratory, vital signs) will be summarized with descriptive statistics. Clinically significant abnormal values will be flagged and tabulated based on predefined criteria. Exposure will be analyzed by describing dose intensity, which is defined as the dose-received divided by the dose planned over a given time interval. This will be done by cycle as well as overall cycles received for epacadostat and pembrolizumab. For each cycle, incidences of dose reductions and cycle

delays will also be tabulated, by reason for the reduction or delay. The percentage of subjects with any delay and/or reduction will also be calculated.

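### Section 12.2.1 has no PFS rule for new anticancer therapy before documented progression, and its censoring dates, read literally, can credit unscanned time as progression-free

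*Combined protocol and SAP*

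**What the plan says.** **The test.** Section 12.1 sets the design: "We will enroll 30 patients over 18 months and follow patients for at least 6 months". It adds that "A 6-month PFS of 20% was observed using single agent pembrolizumab and is the basis for the null hypothesis of the present study". The test is binomial, one-sided at 10%, with a stated 80% power at a true rate of 39%.

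**The endpoint and its censoring.** In Section 12.2.1 and Table 8 a PFS event is progression or death; starting another therapy is not an event. Section 12.2.1 adds that "patients who drop out will be censored at the point of last follow up", without defining either the drop-out or the follow-up it means. Section 12.3, in the paragraph on overall survival, speaks of time-to-event data in general, "treating subjects with no observed death or progression as censored at their last date known to be alive".

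**When scans stop.** Section 4.9.2 says: "Imaging should continue to be performed until documented disease progression, the start of new anticancer treatment", followed by other stopping reasons. Section 4.6.2 has the same stop. Section 4.3.7.3 says: "Once new anti-cancer therapy has been initiated, the subject will move into survival follow-up". In that phase, per Section 4.6.3, "the subject moves into the survival follow-up phase and should be contacted by telephone every 12 weeks", and the call is for survival status.

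**What is known about the switch.** Section 4.6.2 says: "Information regarding post-study anti-neoplastic treatment will be collected if new treatment is initiated". The PFS definition does not use this information. For immune-related best response, Section 14.8.7 does stop at the last tumor assessment before subsequent therapy. PFS has no such cut-off.

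**The concern.** A patient may stop treatment for toxicity or intolerance, without a scan that meets progression, and start another therapy before 6 months. From then on the plan collects survival, not tumor status. If PFS is censored at the last contact of any kind, the time between the last scan and the last telephone call counts as progression-free although no one looked.

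For example, take a patient with a clean scan at week 9 who stops and switches at week 12 and is alive at the second 12-weekly call, at week 12 + 24 = 36. That patient would carry 36 progression-free weeks, of which 36 − 9 = 27 have no tumor assessment behind them. Six months is about 26 weeks, so the patient would pass the landmark.

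The direction is one-sided: such credit can only raise the 6-month rate, toward rejecting the 20% null. The trial is open-label and single-arm, and the binomial test needs a yes or no for every patient. Without a written rule, that status may be settled after the data are known.

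**Working it through.** **Inputs.** n = 30, null 20%, alternative 39%, one-sided 10%, binomial (Section 12.1). The 6-month overall survival of 66% is from the pembrolizumab cohort described in Section 2.1; it is used only as an illustrative share of switchers alive at 6 months. The documents give no rate of switching before progression, so k = 1, 2 or 3 of 30 is an assumed range.

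**Step 1: the plan's own figure.** With X ~ Bin(30, p), find the smallest r with P(X ≥ r) ≤ 0.10 at p = 0.20.
- r = 9: 0.129, above 10%.
- r = 10: 0.061, so the rule is at least 10 of 30.
- Power at p = 0.39 with r = 10: 0.793, which reproduces the stated 80%.

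**Step 2: one patient at the boundary.** Nine documented progression-free patients give p = 0.129 and no rejection. One switcher counted as progression-free makes it 10 of 30, p = 0.061, and the null is rejected.

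**Step 3: false-positive rate.** Let the true rate be 20%. Suppose that on average k of 30 patients are true failures who switch early, and that a share s of them is alive past 6 months and counted as progression-free. The apparent rate is 0.20 + (k/30) × s, and the false-positive rate is P(X ≥ 10) at that rate.

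| k | s = 1: apparent rate | false-positive rate | s = 0.66: apparent rate | false-positive rate |
|---|---|---|---|---|
| 0 | 20.0% | 6.1% | 20.0% | 6.1% |
| 1 | 23.3% | 14.1% | 22.2% | 10.9% |
| 2 | 26.7% | 26.2% | 24.4% | 17.5% |
| 3 | 30.0% | 41.1% | 26.6% | 25.9% |

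As a check on the model, fix exactly k such patients and keep the overall true rate at 20%. The other 30 − k then have rate 6/(30 − k), and the false-positive rate is P(Bin(30 − k, 6/(30 − k)) ≥ 10 − k) = 12.8%, 23.8% and 39.3% for k = 1, 2, 3. The s = 1 column does not depend much on how k is modelled.

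**Step 4: price of the strict rule.** If k switchers count as not progression-free and the other 30 − k have a 39% rate, power is P(Bin(30 − k, 0.39) ≥ 10) = 0.752, 0.705 and 0.653 for k = 1, 2, 3, against 0.793 with none. If the switchers are true failures under the null, counting them as failures leaves alpha at its design value of 0.061.

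**The case against.** A reader might infer that the plan carries every early switcher as progression-free past 6 months. The documents do not say that. A switcher who stays in survival follow-up is not clearly a drop-out. Sections 4.6.2 and 4.6.3 separate disease follow-up from survival follow-up, so the censoring date in Section 12.2.1 could mean the last disease assessment. The Section 12.3 wording stands under overall survival. Section 12.1 is silent on censored patients, who could equally be counted as failures, excluded or handled by Kaplan-Meier. All of this stands: the carry-forward is permitted, not prescribed.

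The affected group is also smaller than all switchers.
- Footnote 9 of the Schedule of Events asks for a scan at discontinuation without confirmed progression, and this will document progression in some. It is waived if a scan was done in the prior 4 weeks, as in the week-9 and week-12 example, and it cannot show progression that comes later.
- Deaths before 6 months remain events.
- Table 8 limits PFS to patients with the first 9-week scan, which removes the earliest switchers. That conflicts with the intent-to-treat statement in Section 12.2.1, and it does not remove a week-12 switcher.
- Median PFS in the cited cohort was 1.9 months (Section 2.1). If the same holds here, many failures will be seen by the first scan.

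Finally, the documents do not say how the source of the 20% null treated switchers, so a strict rule could tilt the comparison the other way. This is a reason for a sensitivity analysis, not for leaving the rule unwritten.

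**Conclusion.** The concern holds in limited form. Imaging stops at new therapy, the stated censoring dates are not tied to a tumor assessment, and nothing says how a switcher without documented progression enters the binomial test. Applied as written, those dates can credit unscanned time and bias PFS upward.

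With a cut-off of 10 of 30, a single patient can decide the result. The 14%, 26% and 41% are a worst case: they assume that 1, 2 or 3 of 30 true failures switch early, that all are alive past 6 months and that all are counted as progression-free. With 66% alive the figures are about 11%, 18% and 26%. The 66% is a whole-cohort figure, not one for switchers, and the number of switchers is an assumption throughout. The documents do not support a claim that the type I error of this trial is inflated by any particular amount.

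**What to change.** 1. In Section 12.2.1, censor Kaplan-Meier PFS at the last adequate tumor assessment on or before the start of new anticancer therapy or loss to follow-up.
2. In Section 12.3, limit censoring at the date last known alive to overall survival.
3. For the binomial test, state that a patient without a tumor assessment showing no progression at the 6-month time point is not counted as progression-free. Name the scan that serves: with scans every 9 weeks the nearest is week 3 × 9 = 27, with its window.
4. Add a sensitivity analysis under the alternative handling, for example the 6-month Kaplan-Meier estimate with the censoring in item 1.

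The imaging and follow-up sections need no change, and no scans or visits are added. The cost is an amendment to Section 12 (Section 11.1 requires IRB approval), a slightly lower 6-month estimate, and power of about 75%, 71% or 65% if 1, 2 or 3 switchers count as failures and the rest have 39% PFS. The amended text should state that loss of power.
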